2.0 TRIAL DESIGN

2.1 Trial Design

This is a Phase I/Ib investigator-initiated open label trial of the combination of VESANOID and pembrolizumab treatment.

A total of 24 evaluable patients will be recruited into the study. All the patients will receive 200mg Q3W pembrolizumab treatment plus the supplemental treatment of 150 mg/m² VESANOID orally for 3 days surrounding each of the first four infusions of pembrolizumab (day -1, day 0, day +1) for a total of 12 days of VESANOID treatment (Section 2.2 *Trial Schema/Diagram*).

To closely monitor DLTs, subjects will be recruited into the study using a cohort size of 6. The toxicity monitoring design is to inform de-escalation decisions based on safety if needed. DLTs will be assessed during the DLT assessment window of 21 days following the first dose of Vesanoid and Pembrolizumab (Cycle 1 Day 0 to Cycle 2 Day 0). Patients who withdraw from the study prior to completing the DLT assessment window for any reason other than a DLT will be replaced. See Section 6.1.1.2.3 for DLT definition.

After the first 6 subjects in cohort 1 complete the DLT period, the Sponsor-Investigator will review data pertaining to the dose de-escalation decision. Available adverse event data and laboratory assessments will be used to determine whether the Vesanoid dose should be continued at 150 mg/m^2 or whether the Vesanoid dose should be de-escalated to 100 mg/m^2 in the subsequent six subjects to be enrolled in cohort 2.

Dose de-escalation will proceed in accordance with the following rules:

- 6 patients will be treated in cohort 1.
 - If 0-2 patients experience a DLT in cohort 1, the Vesanoid dose will be maintained.
 - \circ If \geq 3 patients in cohort 1 experience a DLT, then dose de-escalation of Vesanoid will proceed.
- 6 additional patients will be treated in cohort 2 at either the starting Vesanoid dose (150 mg/m²) or the reduced Vesanoid dose (100 mg/m²).
 - If 0-2 patients experience a DLT in cohort 2, the Vesanoid dose will be maintained.
 - If \geq 3 patients in cohort 2 experience a DLT, then the study will stop.
- If it is determined that the dose will be maintained from Cohort 2, then an additional cohort (cohort 3) of up to 12 patients (depending on the number of patients required to achieve the enrollment goal of 24 patients, but not to exceed 30 patients) will be treated at either the starting Vesanoid dose (150 mg/m²), or the reduced Vesanoid dose (100 mg/m²).

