6.6.5 Toxicity and Study Discontinuation Criteria

The trial stopping criteria outlined in the Calculated Trial Stopping Criteria (Table 5) below will be followed to avoid posing undue risk to additional patients. Twenty-four patients will potentially be recruited in our study to evaluate DLTs and suggest RP2D. Toxicity is defined as AEs of grade 3 or higher. Historical data of similar patients show an overall grade 3 or 4 toxicity rate of approximately 14% for pembrolizumab treatment alone. It is estimated that the current trial (the combination) may increase toxicity rates an additional 10% compared to pembrolizumab alone. The DSMC will have oversight responsibilities for reviewing toxicities in patients associated with this trial.

Number of Patients	Stopping Criteria	Dosing Action
6 (Cohort 1)	>=3	Dose de-escalate in Cohort 2 (dose level -1)
6 (Cohort 2)	>=3	Study Stop

Table 5 Calculated Trial Stopping Criteria

If the grade 3 or 4 toxicity exceeds 33% the stopping criteria, the next 6 enrolled patients will be put on the lower dose.

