8.0 STATISTICAL ANALYSIS PLAN

The primary goal of the study is to characterize the safety and establish the recommended phase 2 dose (RP2D) and preliminary efficacy evaluation with a total of 24 evaluable subjects. A modified 3+3 design with a cohort size of 6 with a continuous toxicity monitoring. The design is to inform de-escalation decisions based on safety if needed. For the purposes of this trial, a target toxicity rate of approximately 33% will be used to establish the RP2D. Table 7 below provides the probability of detecting the number of DLTs based on true toxicity rates with 24 subjects:

Table 7 Number of DLTs and the Corresponding Cumulative Probability for SeveralToxicity Rates with 24 Subjects

True toxicity rate (%)	Corresponding Number of	Cumulative Probability for
	DLTs (# DLT)	Detecting #DLT
20	5	0.66
25	6	0.56
30	7	0.56
35	8	0.53
40	10	0.65

Safety Analyses

All patients who received any protocol therapy will be employed for safety analyses. Patient incidence of all treatment-emergent AEs will be tabulated by dose and system organ class and preferred term. Tables of fatal adverse events, serious adverse events, treatmentrelated AEs, and adverse events leading to withdrawal from investigation product will also be provided. The MedDRA will be used to code adverse events and the NCI CTCAE version 4.0 will be used to grade severity of adverse events and laboratory toxicities.

Summary statistic will be provided for total number of subjects treated under each dose, average dose administered, and duration of treatment.

For select laboratory parameters, changes of laboratory values over time (eg, change from baseline summary statistics), grade shifts in laboratory values from baseline to worst onstudy value, and grade 3 or higher laboratory toxicities will be summarized. The ECG measurements from this study will be performed as per standard of care for routine safety monitoring.

Efficacy analysis

The efficacy analysis population consists of all subjects who receive at least one cycle treatment (3-day doses of study treatment).

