10.3 Data and Safety Monitoring and Oversight

10.3.1 Data Safety Monitoring Committee and Plan

The Sponsor-Investigator will be responsible for monitoring the trial per the trial monitoring plan, in addition to overseeing the safety and efficacy of the trial including any specimens collected, executing the data and safety monitoring (DSM) plan, and complying with all reporting requirements to local and federal authorities. This oversight will be accomplished through additional oversight from the Data and Safety Monitoring Committee (DSMC) at the University of Colorado Cancer Center (CU Cancer Center). The DSMC is responsible for ensuring data quality and study subject safety for all clinical studies at the CU Cancer Center, which is the coordinating institution of this trial. A summary of the DSMC's activities is as follows:

- Conduct of internal audits
- Ongoing review of all serious adverse events (SAEs), unanticipated problems (UAPs) and reportable adverse events (AEs)
- Has the authority to close and/or suspend trials for safety or trial conduct issues
- May submit recommendations for corrective actions to the CU Cancer Center's Executive Committee

Per the CU Cancer Center Institutional DSM Plan, SAEs, UAPs and reportable AEs are reported to the DSMC, IRB and the Sponsor-Investigator per protocol. All SAEs, UAPs and reportable AEs are to be reported to the DSMC within 5 business days of the investigator receiving notification of the occurrence.

Each subject's treatment outcomes will be discussed by the investigator and appropriate staff at weekly meetings. Toxicity will be addressed in real time and communicated to the team, then submitted to DSMC as indicated. Data regarding number of subjects, significant toxicities, dose modifications, and treatment responses will be discussed.

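### Cohort 3 (up to 12 of 24 patients) has no DLT boundary, and the final DLT count is never set against the 33% target that is to establish the RP2D

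*Combined protocol and SAP*

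**What the plan says.** Section 2.1 treats 6 patients in cohort 1 and 6 in cohort 2. With 0 to 2 DLTs the dose is kept. With 3 or more, cohort 1 leads to 100 mg/m², while for cohort 2 the rule is that if 3 or more "patients in cohort 2 experience a DLT, then the study will stop". If cohort 2 keeps its dose, "then an additional cohort (cohort 3) of up to 12 patients" follows at that dose, and no rule is attached to it. Table 5 (Section 6.6.5) likewise has rows for cohorts 1 and 2 only.

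Under Table 5 stands: "If the grade 3 or 4 toxicity exceeds 33% the stopping criteria, the next 6 enrolled patients will be put on the lower dose". The same section says "Toxicity is defined as AEs of grade 3 or higher" and, on the purpose of the sample, "Twenty-four patients will potentially be recruited in our study to evaluate DLTs and suggest RP2D".

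Section 8.0 describes "A modified 3+3 design with a cohort size of 6 with a continuous toxicity monitoring" and states that "a target toxicity rate of approximately 33% will be used to establish the RP2D". Its safety analyses tabulate events. Table 7 lists binomial probabilities for 24 subjects and attaches no decision to them.

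Section 10.3.1 provides weekly team review of toxicity and a DSMC that "Has the authority to close and/or suspend trials for safety or trial conduct issues".

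**The concern.** The first two cohorts carry explicit counts, but the largest block of patients, half the planned sample, carries none. The phrase about continuous monitoring in Section 8.0 comes without a boundary.

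The MTD and RP2D are the primary objective (Section 3.1), and Section 6.6.5 gives all 24 patients a role in suggesting the RP2D. A dose could pass two checks of 6 by chance, accumulate DLTs well above one third in cohort 3, and still be reported as the RP2D with every written rule respected. At stake are the dose given to the last patients and the basis of the primary conclusion.

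**Working it through.** **Inputs.** Cohort sizes 6, 6 and up to 12, with the dose kept at 0–2 of 6 (Section 2.1). Target about one third (Section 8.0). Planning rate 24% = 14% + 10 points (Section 6.6.5), read as additive and used as a stand-in for the 21-day DLT rate. The rates 40, 50 and 60% are assumptions for a dose above target. Patients at one dose are taken as independent with a common DLT rate p.

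**The plan's own figures.** Table 7 is closest to P(X ≤ d) with n = 24. That gives 0.6559, 0.6074, 0.5647, 0.5257 and 0.6502, against the stated 0.66, 0.56, 0.56, 0.53 and 0.65. Four rows reproduce; the 25% row does not (about 0.61 against 0.56). Nothing below depends on that row. The table contains no rule for acting on a count.

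**Step 1: what the written rules tolerate.** At 150 mg/m²: 2 + 2 + 12 = 16 of 24 (67%). At 100 mg/m², where only cohorts 2 and 3 contribute: 2 + 12 = 14 of 18 (78%).

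**Step 2: chance of reaching cohort 3 at 150 mg/m².** With a = P(X ≤ 2 of 6), the chance is a². For p = 24, 33.3, 40, 50 and 60%: 0.846² = 0.716; 0.680² = 0.463; 0.544² = 0.296; 0.344² = 0.118; 0.179² = 0.032.

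**Step 3: cut-offs from the sponsor's own one third.** Since 2 of 6 keeps the dose, action starts above one third. One third of 18 is 6, so act at 7; of 24 is 8, so act at 9; of 12 is 4, so act at 5.

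**Step 4: the n = 18 look, worked at p = 40%.** Let S be the DLTs in cohorts 1 and 2 given 0–2 in each, and U the DLTs in the first 6 of cohort 3. P(S = 1, 2, 3, 4) = 0.0588, 0.2155, 0.3918, 0.3265. P(U ≥ 6, 5, 4, 3) = 0.0041, 0.0410, 0.1792, 0.4557. Then P(S + U ≥ 7) = 0.0588×0.0041 + 0.2155×0.0410 + 0.3918×0.1792 + 0.3265×0.4557 = 0.228. Over all trials: 0.2281 × 0.2963 = 0.068.

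**Step 5: all rates at 150 mg/m².** The columns marked "reached" are percentages of trials that reach cohort 3.

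| True DLT rate | Reach cohort 3 | ≥7/18, reached | ≥7/18, all trials | Final ≥9/24 with no look, reached | Either look, reached | Either look, all trials |
|---|---|---|---|---|---|---|
| 24% | 0.716 | 2.9% | 2.1% | 3.4% | 4.8% | 3.4% |
| 33.3% | 0.463 | 11.7% | 5.4% | 17.3% | 20.6% | 9.5% |
| 40% | 0.296 | 22.8% | 6.8% | 35.2% | 39.1% | 11.6% |
| 50% | 0.118 | 44.8% | 5.3% | 66.0% | 69.0% | 8.1% |
| 60% | 0.032 | 68.0% | 2.2% | 88.4% | 89.6% | 2.9% |

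**Step 6: failing only at the final count.** Either look minus the n = 18 look, among trials reaching cohort 3: 20.58 − 11.74 = 8.8% at 33.3%, and 39.06 − 22.81 = 16.3% at 40%. In these trials 150 mg/m² exceeds one third and nobody has been assigned to start at 100 mg/m².

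**Step 7: 100 mg/m², given 0–2 of 6 in cohort 2.** P(≥5/12) = 6.7, 19.6, 32.5, 54.6 and 75.0% at the five rates. With the final check at 7 or more of 18 added: 10.2, 30.9, 50.2, 76.8 and 92.8%.

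**The case against.** The best defence is that the target is already in use: keeping the dose at 2 of 6 and acting at 3 of 6, twice, applies one third to 12 patients before cohort 3 opens. On that view cohort 3 is a Phase Ib expansion, which Section 6.1.1.2.3 describes as further safety evaluation and preliminary efficacy, and a boundary there is partly a design preference. The first half stands, so a reader should not infer that the 33% target is never applied. The second half does not dispose of the point, because Section 6.6.5 assigns all 24 patients to evaluating DLTs and suggesting the RP2D.

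A reader might also infer that the sentence under Table 5 is a rival rule that would lead two investigators to dose the same cohort 3 patients differently. The documents do not support this. The sentence refers to the stopping criteria directly above it; more than 33% of 6 is 3 or more; and the next 6 patients on the lower dose is what the cohort 1 row orders. Most plainly it restates that row, without conflict with the cohort 2 stop. Only if it was meant to reach cohort 3 do problems arise: it has no denominator, it counts grade 3 or 4 toxicity where Section 6.1.1.2.3 defines DLTs differently, and it has no action for patients already at 100 mg/m².

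Nor does the gap mean that cohort 3 is unsupervised. Weekly review and DSMC powers (Section 10.3.1), individual holds and reductions (Section 6.1.1.2.3) and early termination for a health hazard (Section 6.6.6) all apply. They are discretionary or individual, and none sets a cohort-level count.

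Finally, the benefit is limited. The one look that changes a dose acts in 5.4% of all trials at the 33% target, about as often as at 50% (5.3%). That stands, and it sets the weight of the point.

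**Conclusion.** The point holds. Cohort 3 has no DLT boundary, and no stated rule links the final cumulative count to the 33% target. The first matters for the dose of the last patients, the second for the primary conclusion.

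The size is modest. The two existing checks already screen out most clearly toxic doses: at a true 50% only 12% of trials reach cohort 3 at 150 mg/m², and at 60% only 3%. At the planning rate of 24%, a final count above one third is rare (3.4% of trials reaching cohort 3). The exposure is greatest in the middle: at a true 40%, 30% of trials reach cohort 3, and 35% of those end above one third with no stated consequence.

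These figures assume a common, independent DLT rate at each dose, an additive reading of the 10% increase, and 24% as a stand-in for the 21-day DLT rate. The absence of a boundary does not depend on them. It should be fixed because the remedy is cheap and the RP2D is the primary objective.

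**What to change.** 1. **Section 2.1 and Table 5.** Add a cohort 3 row, checked on cumulative DLTs at the dose in use after the first 6 cohort 3 patients. At 150 mg/m², 7 or more of 18 pauses enrolment for DSMC review and puts the next 6 on 100 mg/m² under the existing 3-of-6 rule. At 100 mg/m², 5 or more of 12 pauses enrolment for DSMC review, with any stop left to the DSMC. State that the sentence under Table 5 applies to cohort 1.

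2. **Section 8.0.** State that a dose is recommended as RP2D only if its final cumulative DLT proportion is at most one third (8/24 at 150 mg/m², 6/18 at 100 mg/m²), reported with an exact 95% CI. If 150 mg/m² exceeds this only at the final count, report that it exceeds the target and that no RP2D is established without further data at 100 mg/m².

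The exact counts are the sponsor's choice if fixed in advance. For example, 8 or more of 18 cuts flags at the 33% target from 11.7% to 3.1% of trials reaching cohort 3, but then catches only 7.5% at a true 40% and 20.3% at 50%.

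**Cost.** Wording and table rows, plus up to one 21-day wait with DSMC review. With both looks at 150 mg/m², false flags occur in 5% (true 24%) and 21% (true 33%) of trials reaching cohort 3, or 3.4% and 9.5% of all trials. At 100 mg/m² the pause alone is triggered in 7% and 20% of trials continuing at that dose. A flag at n = 18 leaves only 6 of the 24 patients for 100 mg/m², where 2 of 6 has an exact 95% CI of 4 to 78%.

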2.2 Trial Schema/Diagram

Proposed schedule for treatment and blood draws.

Figure 1. Diagram of the treatment and blood draw schedule for this study. Patients will receive pembrolizumab infusions every three weeks. Patients will also receive 3 days of VESANOID treatment surrounding each of the first 4 infusions of pembrolizumab, beginning one day prior to the infusion (a total of 12 days of VESANOID). Six tubes of peripheral blood (for a total of approximately 40 ml) will be drawn at enrollment, at the 2rd and 4th infusions, and within 60 days of the final VESANOID dose for additional functional experiments.

3.0 OBJECTIVE(S) & HYPOTHESIS (ES)

3.1 **Primary Objective**

To identify the MTD and RP2D of the combination of pembrolizumab and ATRA.

3.2 Secondary Objective:

- Describe the safety and toxicity of combined treatment with pembrolizumab and alltrans retinoic acid (ATRA) [brand name VESANOID] in melanoma patients.
- To assess the anti-tumor activity in terms of a). The reduction in MDSC (immunosuppressive myeloid –derived suppressor cells) frequency and suppressive function (measured as a continuous variable) in peripheral blood of advanced melanoma patients undergoing pembrolizumab and VESANOID combination therapy. b). progression free survival.

3.3 Exploratory Objective

To determine the clinical outcomes with tumor-specific T cell responses.

4.0 BACKGROUND & RATIONALE

4.1 Background

Melanoma elicits profound immune responses and is one of the few tumors for which immunotherapies have been successful (1). However, melanoma counters current immunotherapeutic approaches by inducing immune escape mechanisms, a critical barrier that may contribute to low response rates and treatment failure (1). Melanoma continues to be a leading cause of death among adult cancer patients (2, 3). Furthermore, the incidence of melanoma continues to increase across all age groups (4).

The antibody therapy pembrolizumab, specific for programed cell death receptor 1 (PD-1), an inhibitory molecule expressed on activated T cells, has recently been shown to significantly improve overall survival and induce durable, long-lasting responses in approximately 45% of treated patients (5). Since pembrolizumab was granted approval as a first line treatment in metastatic melanoma patients, it has largely replaced Ipilimumab due to higher response rates with lower toxicities (5). While the results of this monumental study highlight a crucial advantage of immunotherapies in achieving long-term immunity that is resistant to disease relapse, increased response rates to pembrolizumab could further enhance survival and clinical outcomes for patients with advanced-stage melanoma. One proven mechanism of action for this drug is eliciting the frequency and function of tumor-specific T cells (6). However, tumor induced immunosuppression may limit the development of effective immune responses in some patients treated with pembrolizumab. Improving clinical responses to pembrolizumab by enhancing other immune-mediated mechanisms in a combinatorial approach is essential for the future evolution of immunotherapeutic strategies.

MDSCs are a mixed population of immunosuppressive myeloid cells that are key contributors to tumor-induced immunosuppression. Increased numbers of MDSCs are associated with larger tumor burdens, increased tumor progression, and shorter overall survival in several cancers, including melanoma (7-10). These data suggest that targeting MDSCs may improve tumor-specific immune responses, increase clinical responses to immunotherapy, and ultimately increase survival in melanoma patients. In this proposal, we aim to decrease the frequency and/or function of MDSCs in melanoma patients treated with all-trans retinoic acid (ATRA).

4.1.1 Pharmaceutical and Therapeutic Background

All-trans retinoic acid (ATRA) is a vitamin A derivative that binds the retinoic acid receptor on MDSCs and differentiates immature monocytes into more mature dendritic cells (11). VESANOID is a standard treatment currently approved for patients with acute promyelocytic leukemia (APL).

VESANOID (tretinoin) is an FDA-approved commercially available retinoid that induces maturation of APL cells in culture. It is not approved in combination with pembrolizumab or for the treatment of patients with melanoma. It is available in a 10 mg soft gelatin capsule for oral administration. The recommended dose (for APL) is 45 mg/m2/day administered as two evenly divided doses until complete remission is documented.

Virtually all patients with APL experience some drug-related toxicity, especially headache, fever, weakness, and fatigue. These adverse effects are seldom permanent or irreversible nor do they usually require interruption of therapy. Some of the adverse events noted in patients with APL are associated with rapid tumor response and include hemorrhage, infections, gastrointestinal hemorrhage, disseminated intravascular coagulation, pneumonia, septicemia, and cerebral hemorrhage. There are no reported adverse side effects in patients with solid tumors treated with a short course of 150 mg/m² VESANOID combined with high dose IL-2 or a dendritic cell vaccine (*12, 13*).

4.1.2 Preclinical and Clinical Trial Data

Pre-clinical data suggest that VESANOID abrogates the suppressive effects of MDSCs isolated from both human cancer patients and mouse cancer models in vitro (14-16). Furthermore, mice treated with VESANOID have decreased frequencies of MDSCs and increased frequencies of dendritic cells that improve T cell responses against tumors (17-19).

Our preliminary research has identified a population of immunosuppressive MDSCs (Lineage negative, HLA-DR negative, CD11b positive, and CD33 positive) that are increased in Stage IV melanoma patients relative to healthy donors. To establish MDSCs as a potentially important contributor to immunosuppression in melanoma patients, we compared the frequency and function of immunosuppressive MDSCs in the peripheral blood of healthy donors, Stage I, and Stage IV melanoma patients (10). We found significant increases in the frequency of MDSCs in the peripheral blood of Stage IV

melanoma patients compared to healthy donors. We showed that the frequency of these cells correlates with an increase in regulatory T cells and an increased level of IL-6 and IL-8 cytokines in the peripheral blood. Furthermore, patients with clinical disease progression had an increased frequency of these cells. We also found that patients with a high frequency of MDSCs had decreased overall survival and an increased risk of death (hazard ratio 4.83, p = 0.016). This increased risk of death was independent of other clinical factors including age, gender, and treatment regimens. Finally, we demonstrated that MDSCs isolated from Stage IV melanoma patients were significantly more immunosuppressive than those isolated from healthy donors. Overall, these data suggest that MDSCs may be a significant contributor to immunosuppression in melanoma patients and that targeting these cells in a combinatorial approach may improve immune responses against melanoma.

VESANOID induces the differentiation of immature monocytes into more mature cells of the dendritic cell lineage (15, 16, 20). In agreement with these results, our preliminary data suggest that VESANOID induces maturation of in vitro-derived MDSCs. We cultured monocytes from healthy donors with GM-CSF/IL-4 or GM-CSF/IL-6 to generate mature monocytes of the dendritic cell lineage (a control population) or MDSCs, respectively (21, 22). In contrast to the control population, MDSCs express low levels of HLA-DR and maintain high expression of CD14, consistent with the phenotype of an immature monocyte. Furthermore, MDSCs express increased levels of molecules that inhibit T cell responses such as Arginase I, NOX1, iNOS, and PD-L1. Conversely, MDSCs cultured with VESANOID are phenotypically more similar to the control dendritic cell population, expressing decreased levels of inhibitory molecules and CD14 and increased levels of HLA-DR. Most importantly, MDSCs derived in vitro with GM-CSF and IL-6 suppress T cell proliferation. However, treatment of these MDSCs with VESANOID eliminates their suppressive effects and restores T cell proliferation. Finally, MDSCs express higher levels of retinoic acid receptors RAR and RXR, suggesting that VESANOID treatment may selectively target these inhibitory cells. These preliminary data and our previous publications demonstrate that our research team has established the protocols necessary to accomplish the experiments outlined in this protocol.

